7.4.2 Positron-emission tomography (PET) imaging

7.4.2.1 11C-PIB PET imaging

Amyloid tracer [N-methyl-11C]2-[4'-(methylamino) phenyl]-6-hydroxybenzothiazole (11C-PIB) is the mostly studied and relatively mature Phenothiazine A β imaging agent, which is a 11C-labeled derivative of Thioflavin-T. It can specifically bind to A β plaques in the brain of AD patients and is used for positioning and quantitative analysis of A β in brain. 11C-PIB PET can differentiate AD and normal patients in the early and middle stages of the disease, reflect the pathological changes of brain tissue, provide more objective data for early diagnosis. Further combined with clinical history, laboratory tests, neuropsychology scale and structural imaging results, it can help improve the accuracy of the diagnosis to guide early treatment. Image acquisition is completed by radiology department of each center, stored and transmitted in DICOM format, and then image processing is carried out to obtain whole brain and regional standard uptake value ratio (SUVR), and used as location and quantitative indicators of A β deposition.

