2.2 Research sites

There is a total of 68 research centers participating in this project, involving 26 provinces and cities. For details, please refer to Appendix 16.

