2.3 Research period

The research period of this project is from February 2005 to January 2038 or longer.

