2.4 Sample size

There will be a total of 40,000 subjects participating in this project. The total number of subjects to be included in this hospital is 5,000, and other sites include 400-600 persons per sites.

3. Research aims

This research will establish and continuously improve the FAD research network in conjunction with multi-center institutions nationwide. By collecting information on the family's demography, genetics, neuropsychology, neuroimaging, biomarkers and other information, we can understand the current FAD population in China, clarify the genetic characteristics, pathogenesis, disease characteristics and diagnosis and treatment status of AD in China; which will lay the foundation for ameliorating clinical diagnosis and treatment, establishing a Chinese FAD clinical database and an international cooperative research platform.

3.1 To set up a multi-center, nationwide FAD research network and database platform in China

The network and database include ADAD cohort of the known mutations of *PSEN1*, *PSEN2* and *APP* (mutation carriers and noncarriers; pre-symptomatic and symptomatic) and unknown mutations cohort.

3.2 To clarify the epidemiological characteristics of FAD in China.

Conduct a comprehensive FAD epidemiological survey in China to clarify the impact of different nationalities, regions, gender, age, living environment (rural/urban), education level, etc. on the

occurrence and development of the disease.

3.3 To clarify the genetic characteristics of FAD in China.

This project is to discover new FAD mutation sites, pathogenic genes, to protective genes, to explore the pathogenic and protective mechanism, to analyze the disease development laws of families with different sizes of FAD in China, and to clarify the frequency distribution of mutant genes in the Chinese FAD population.

3.4 To clarify the clinical characteristics and disease development laws of FAD in China.

The project will collect and regularly follow-up the samples (blood, urine and saliva etc.) and data (neuropsychology, imaging etc.) in the cohort. Emphasis is placed on the occurrence and development of asymptomatic mutant gene carriers from asymptomatic to symptomatic periods.

3.5 To discover and verify the early diagnosis biomarkers of AD.

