4.5.2 Image markers

We follow up the subjects with normal cognitive, Pre-MCI, MCI, AD stages in the FAD family, and test the hippocampus atrophy and cortical thickness of the subjects by MRI. We also detect eight observation brain regions by ^{18}F -FDG PET (bilateral frontal lobe, bilateral temporal lobe, bilateral parietal lobe, bilateral hippocampus). We will obtain accurate registration image data of patients' brain structure, metabolic function, pathological protein molecule deposition at various stages of AD progression. We will determine the quantitative critical thresholds for the early diagnosis of AD by ^{18}F -FDG PET and ^{11}C -PIB PET. Then we will obtain highly sensitive imaging markers for the early diagnosis of AD.

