7.4.3 Carotid ultrasound

Carotid ultrasound can clearly demonstrate the vascular intima-media thickness, the location and size of plaque, the degree of vascular stenosis, and analyze hemodynamics. It plays a key role in the assessment and diagnosis of vascular-related diseases caused by atherosclerosis. Carotid ultrasound examination should be performed within 1 month before or after neuropsychological examination (with no new vascular disease event). An experienced ultrasound physician is required to perform the operation according to "Guidelines for Carotid Ultrasound Examination". Longitudinal and transverse

section scanning are performed from frontal and lateral directions. Observe and record the peak systolic velocity (PSV), end diastolic velocity (EDV), intima-media thickness (IMT) and plaque (diameter, number, acoustic properties) of internal carotid artery, common carotid artery and carotid bifurcation.

8. Statistical analysis

Periodic review of the accumulating data will be made to safeguard the statistical quality of the data and to ascertain whether they conform to the expectations of the original statistical design. At the same time, the statistician will perform statistical quality control of FAD data, focusing on outlier and missing data detection and comparison among sites. Then, the statistician will participate in statistical data analyses, consultations and reporting using R software and other statistical software, such as SAS and SPSS for specialized statistical analyses. The sample size is calculated using the paired sample t test, and the statistical test level is set to 0.05.

The normality and homogeneity of variance tests were performed on continuous variables. Data that passed these two tests were presented as mean \pm standard deviation, then underwent t-testing for comparisons between two groups and one-way analysis of variance (ANOVA) testing for comparisons among three or more groups. After ANOVA analysis, a Dunnett's multiple comparison test was used for post hoc testing. Data that did not pass the normality test were presented as quartiles, and underwent nonparametric testing, using the Kruskal-Wallis test and Dunn's multiple comparison test for comparisons among three or more groups. The significance of differences was assessed by the χ^2 test for categorical variables. The correlation between variables were calculated using Pearson or Spearman method.

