For the longitudinal repeated data, to explore the correlation between different markers and AD, a Bayesian linear mixed model was used to model each marker as a function of estimated years from expected symptom onset (EYO) and mutation status (carrier or noncarrier). The fixed effects included sex, age, follow-up time, mutation status, EYO, and their two-way interaction.

9. Data management

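### PET is acquired separately at 68 centres, but Section 8's group tests have no centre term and its listed fixed effects include neither centre nor scanner

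*Protocol*

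**What the plan says.** - **Centres and period.** Section 2.2: "There is a total of 68 research centers participating in this project, involving 26 provinces and cities". Section 2.3: "The research period of this project is from February 2005 to January 2038 or longer". That is 33 years.
- **Acquisition.** Section 7.4.2.1 (PIB) and Section 7.4.2.2 (FDG) use the same words: "Image acquisition is completed by radiology department of each center, stored and transmitted in DICOM format". The images are then processed to whole-brain and regional SUVR.
- **Group comparisons.** For continuous variables, Section 8 names the t test for two groups, one-way ANOVA for three or more, and Kruskal-Wallis where normality fails. No covariate or stratum is given.
- **Longitudinal model.** Section 8 specifies a Bayesian linear mixed model and says: "The fixed effects included sex, age, follow-up time, mutation status, EYO, and their two-way interaction". Random effects are not listed.
- **Use of site.** Section 8 mentions site once, in the statistician's quality control of the data: "focusing on outlier and missing data detection and comparison among sites".
- **Thresholds.** Section 4.5.2, on FDG and PIB PET: "We will determine the quantitative critical thresholds for the early diagnosis of AD". No derivation method is given.

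**The concern.** Systematic measurement differences between centres do no harm to a group comparison if every centre has the same mix of groups. If the mix differs, the pooled difference contains part of the centre differences, and the usual standard error does not allow for them. A t test, ANOVA or Kruskal-Wallis test then rejects a true null hypothesis too often, and more so as the sample grows. Comparing sites as a quality check may reveal an offset, but it does not remove one from the estimate.

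The contrasts are not equally exposed:
- **Autosomal dominant versus unknown-mutation families** is the most exposed. It is a between-family contrast, and Section 6.1 directs online registrants to a centre by geography.
- **Normal, Pre-MCI, MCI and AD** are less exposed. Section 6.2, criteria 2 and 3, requires both affected and cognitively normal members in each family, and relatives will tend to attend one centre.
- **Carrier versus noncarrier within a family** is largely protected for the same reason.
- **Within-person change** is exposed if a participant's serial scans span a scanner replacement, because the step is then read as an effect of follow-up time.

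The diagnostic thresholds are also at stake. A single cut-off performs differently at a centre whose values sit higher or lower.

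**Working it through.** **Inputs from the protocol.** Section 2.4: "There will be a total of 40,000 subjects participating in this project", with 5,000 at the lead hospital and 400 to 600 at each other site. Check: 5,000 + 67 × 400 = 31,800 and 5,000 + 67 × 600 = 45,200. The total of 40,000 needs (40,000 − 5,000)/67 = 522 per site, which fits.

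**Assumed inputs (not in the protocol).**
- Centre offsets have SD τ = 0.2 or 0.3 of the within-group SD.
- One group's share at each centre is drawn from Beta(2,2), Beta(20,20) or fixed at one half. The share has variance 0.25/5 = 0.05 (SD 0.22) under Beta(2,2) and 0.25/41 = 0.0061 (SD 0.08) under Beta(20,20).
- Image numbers are 1,000 + 67 × 100 = 7,700, or 200 + 67 × 20 = 1,540.
- There are two groups with no true difference.

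**Mechanism.** With groups of roughly equal size overall, the variance of the pooled difference is inflated by about

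V = 1 + 4 · Var(share) · τ² · Σn²/N,

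where n is the number of images per centre. The nominal 5% test then rejects with probability about 2Φ(−1.96/√V).

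- 7,700 images: Σn²/N = (1,000² + 67 × 100²)/7,700 = 216.9. Under Beta(2,2) and τ = 0.2, V = 1 + 4 × 0.05 × 0.04 × 216.9 = 2.74, so rejection is about 24%. For τ = 0.3, V = 4.90 and rejection is about 38%.
- 7,700 images, Beta(20,20): V = 1.21 and 1.48, giving about 7% and 11%.
- 1,540 images: Σn²/N = 66,800/1,540 = 43.4. Under Beta(2,2), V = 1.35 and 1.78, giving about 9% and 14%.

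The formula runs high because it takes the overall split as exactly half and averages the variance rather than the rejection rate. Simulation does not have that defect:

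| Setting | τ = 0.2 | τ = 0.3 |
|---|---|---|
| 7,700 images, Beta(2,2) | 20% | 30% |
| 7,700 images, Beta(20,20) | 7% | 9% |
| 7,700 images, equal mix | 5% | 5% |
| 1,540 images, Beta(2,2) | 8% | 11% |
| Any of these, with a centre term | about 5% | about 5% |

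Repeat runs agree to within one or two percentage points.

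**Threshold illustration (also assumed).** Put the cut-off at 95% specificity with AD 2 SD above controls, so that sensitivity is 1 − Φ(1.645 − 2) = 64%. At a centre reading 0.25 SD high, specificity is Φ(1.645 − 0.25) = 92% and sensitivity 73%. At one reading 0.25 SD low, they are 97% and 54%.

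**The case against.** Four stronger readings are tempting, and the protocol does not support them.

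1. *The longitudinal model has no centre term.* Section 8 lists fixed effects only. A mixed model has random effects, and none is named, not even participant. Centre may be among them, and a statistical analysis plan that is not shown could say so. What stands is that centre and scanner are not among the fixed effects the protocol lists, and that the group tests are named without adjustment.

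2. *The PET thresholds come from unadjusted pooled values.* Section 4.5.2 gives no method, so this is inference.

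3. *Every scan comes from an unrelated scanner.* Section 7.4 names GE PET/MR for the lead hospital and each sub-centre, Section 2.1 promises a unified standard, and Section 9.2 sends images to a central archive, which could allow common processing. These may reduce scanner differences. They do not establish harmonisation over 33 years: the equipment list is not exclusive, no calibration or replacement rule is given, and the standardisation in Section 10.2 concerns the neuropsychological tests.

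4. *The error rate is around half.* At full size (5,000 + 67 × 522 images) and Beta(2,2), simulated rejection is about 47% and 60%. That needs the whole cohort in one two-group comparison together with wide imbalance. Under Beta(20,20) it is about 15% and 23%. The family inclusion criteria make wide imbalance less likely for the stage contrasts.

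It is also fair that the tests in Section 8 are generic and are not said to be the only analyses for imaging. They are, however, the only group comparisons of continuous variables that the protocol names.

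**Conclusion.** The point holds in a limited form. As written, cross-centre imaging contrasts would be tested by methods that ignore centre, and the stated fixed effects do not make up for this. Whether the harm is negligible or large depends on two quantities the protocol does not give: the size of the centre offsets and how far group mix varies between centres. Under the assumptions shown, the actual error rate of a 5% test runs from 5% (equal mix) through 7% to 9% (mild imbalance) to 20% to 30% (wide imbalance) at 7,700 images. At 1,540 images it is 8% to 11% under wide imbalance. A centre term restores about 5% in every case, so adjustment is the better choice without knowing which case applies. The size of the error in within-person change cannot be derived from the document.

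**What to change.** - **Section 8, cross-sectional imaging comparisons.** Replace the plain t test, ANOVA and Kruskal-Wallis by a linear model with group and centre, on ranks or transformed values where normality fails. Section 9.2 already puts the site number in the participant code, so this needs no new data.
- **Section 8, longitudinal model.** State a centre effect explicitly. Record the scanner at each scan, and fit a scanner-change indicator as a sensitivity analysis.
- **Section 4.5.2.** Account for centre when the PET thresholds are derived, and check them by leaving out one centre at a time.

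**Cost.** Analysis wording and one recorded field. There are two downsides. Centres contributing only one group add little to the adjusted contrast. A new level at every scanner change could absorb some true within-person change where in-person visits are 3 or 5 years apart (Section 6.6, Table 1), which is why the scanner-change term is proposed as a sensitivity analysis only.

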7.4.2.2 FDG-PET imaging

FDG-PET can detect abnormal brain metabolism in patients with dementia, and should be performed within 1 month before or after neuropsychological examination (with no new vascular disease event). Fasting for at least 6 hours before examination, and fasting blood glucose was measured. Blood glucose levels should be <140 mg / dL (7.8 mmol/L). Image acquisition is completed by radiology department of each center, stored and transmitted in DICOM format, and then image processing is carried out to obtain whole brain and regional standard uptake value ratio (SUVR), and used as location and quantitative indicators of brain metabolic function.

7.4.3 Carotid ultrasound

Carotid ultrasound can clearly demonstrate the vascular intima-media thickness, the location and size of plaque, the degree of vascular stenosis, and analyze hemodynamics. It plays a key role in the assessment and diagnosis of vascular-related diseases caused by atherosclerosis. Carotid ultrasound examination should be performed within 1 month before or after neuropsychological examination (with no new vascular disease event). An experienced ultrasound physician is required to perform the operation according to "Guidelines for Carotid Ultrasound Examination". Longitudinal and transverse

section scanning are performed from frontal and lateral directions. Observe and record the peak systolic velocity (PSV), end diastolic velocity (EDV), intima-media thickness (IMT) and plaque (diameter, number, acoustic properties) of internal carotid artery, common carotid artery and carotid bifurcation.

8. Statistical analysis

Periodic review of the accumulating data will be made to safeguard the statistical quality of the data and to ascertain whether they conform to the expectations of the original statistical design. At the same time, the statistician will perform statistical quality control of FAD data, focusing on outlier and missing data detection and comparison among sites. Then, the statistician will participate in statistical data analyses, consultations and reporting using R software and other statistical software, such as SAS and SPSS for specialized statistical analyses. The sample size is calculated using the paired sample t test, and the statistical test level is set to 0.05.

The normality and homogeneity of variance tests were performed on continuous variables. Data that passed these two tests were presented as mean \pm standard deviation, then underwent t-testing for comparisons between two groups and one-way analysis of variance (ANOVA) testing for comparisons among three or more groups. After ANOVA analysis, a Dunnett's multiple comparison test was used for post hoc testing. Data that did not pass the normality test were presented as quartiles, and underwent nonparametric testing, using the Kruskal-Wallis test and Dunn's multiple comparison test for comparisons among three or more groups. The significance of differences was assessed by the χ^2 test for categorical variables. The correlation between variables were calculated using Pearson or Spearman method.

For the longitudinal repeated data, to explore the correlation between different markers and AD, a Bayesian linear mixed model was used to model each marker as a function of estimated years from expected symptom onset (EYO) and mutation status (carrier or noncarrier). The fixed effects included sex, age, follow-up time, mutation status, EYO, and their two-way interaction.

9. Data management

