Recently, in our study, 3330 patients with AD or mild cognitive impairment in 514 pedigrees were enrolled from the CFAN. 13.12% of pedigrees carried *PSENs/APP* missense mutations, 3.71% carried *PSENs/APP* synonymous/untranslated region variants, and 83.17% did not carry *PSENs/APP* mutations. In the present study, 11 missense mutations were first identified by the CFAN, including 10 in *PSEN1* and one in *APP*. The present study highlights that the FAD population in China needs extensive investigation, and a concerted effort is necessary to identify the crucial pathological genes underlying the pathogenesis of AD.

2. Introduction

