6.1 Participant population

All participants enrolled in CFAN were adults, and at least two first-degree relatives had AD. All participants received clinical assessment and genetic testing at baseline. Based on whether carrying a pathogenic mutation of the *PSEN1*, *PSEN2*, or *APP*, the cohort was further divided into two subgroups: autosomal dominant AD and unknown gene mutation FAD (un-FAD).

Subjects come from three sources:

1) FAD family in the memory clinic of Xuanwu Hospital.

2) FAD family recruited from CFAN subsites, where recruitment was according to the study protocol.

3) Online registration through the CFAN website (www.Chinacfan.org) and submission of basic demographic data and family information to CFAN. The CFAN administrator selects the family that meets inclusion criteria by reviewing the online registration materials, and recommends them to the CFAN subsite or Xuanwu Hospital memory clinic according to the geographical location.

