6.2 Inclusion criteria

(1) Written informed consent obtained from the participant or a legal guardian prior to any study-related procedures;

(2) At least two first-degree relatives in a family have AD (clinically or by testing), and at least 3 out of 2 generations are patients;

(3) At least one family member with normal cognitive function (the age should be greater than the average age of onset of the family);

(4) Pedigrees carrying FAD pathogenic genes (*APP/PSEN1/PSEN2*);

(5) People in this family >18 years old can be recruited;

(6) Participant is cognitively normal or demented but not reaching bedridden level;

(7) Participants are able to provide two reliable informants who can provide clinical information;

(8) Dementia is diagnosed according to the criteria described by the Diagnostic and Statistical Manual of Mental Disorders, Fourth Edition, Text Revision (DSM-IV-R [31]);

(9) The diagnosis of AD is made using the National Institute of Neurologic and Communicative Disorders and Stroke and the Alzheimer's Disease and Related Disorders Association (NINCDS-ADRDA [32]) or National Institute on Aging and the Alzheimer's Association (NIA-AA) criteria [33];

(10) The diagnosis of MCI is made according to Petersen criteria [34] and the classification is according to the method of Lopez et al [35].

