6.5 Baseline visit

The baseline study visit includes the following items:

(1) Explain study contents and procedures to participant and sign the informed consent form.

(2) Urine pregnancy test (for women of childbearing potential).

(3) Check inclusion/exclusion criteria.

(4) Blood, urine and saliva samples collection (biomarkers).

(5) Genetic testing to examine risk gene *APOE* and known pathogenic genes *PSEN1*, *PSEN2*, and *APP* for all participants.

(6) Collecting participant and informant demographics.

(7) Collecting family history and draw family tree.

(8) Previous medical, medication history and life style.

(9) Physical exam and vital signs.

(10) Neurological Exam.

(11) Neuropsychological test: Mini-Mental State Examination (MMSE), Montreal Cognitive Assessment (MoCA), Neuropsychiatric Inventory Questionnaire (NPI-Q), Hamilton Anxiety Scale (HAMA), Hamilton Depression Scale (HAMD), Modified Hachinski Ischemic Scale (m-HIS), the world health organization university of California-Los Angeles auditory verbal learning Test (WHO-UCLA AVLT), Rey-Osterrieth Complex Figure Test (ROCFT), Digit Span Forward (DSF), Digit Span Backward (DSB), Verbal Fluency Test (VFT), Trail Making Test (TMT) A/B, Boston Naming Test (BNT), Clinical Dementia Rating (CDR), Activities of Daily Living (ADL).

(12) MRI includes the following: conventional scan T1 weighted image (T1WI), T2 weighted image (T2WI), T2 FLAIR and hippocampal scan coronary T1-FLAIR sequence.

(13) ¹⁸F-FDG PET.

(14) ¹¹C-PIB PET.

(15) Carotid ultrasound.

(16) Lumbar puncture to examine cerebrospinal fluid (after MRI exams) and follow-up phone call (if participate in LP)

(17) After informed consent, non-pharmaceutical interventions are carried out on non-onset gene mutation carriers in the family, including lifestyle changes, increased physical exercise and cognitive training, and nootropic drugs.

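### Section 8 prescribes tests that assume independent participants, but the cohort is recruited as families, so comparisons between pedigrees reject too often

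*Protocol*

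**What the plan says.** Section 8 fixes the cross-sectional methods. Normally distributed data "then underwent t-testing for comparisons between two groups and one-way analysis of variance (ANOVA) testing for comparisons among three or more groups", with Dunnett's test post hoc. Non-normal data go to Kruskal-Wallis and Dunn, and categorical data to chi-square. For associations, "The correlation between variables were calculated using Pearson or Spearman method". The test level is 0.05.

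The recruitment unit is the family. Section 6.2 requires "At least two first-degree relatives in a family have AD (clinically or by testing), and at least 3 out of 2 generations are patients" (criterion 2) and adds that "People in this family >18 years old can be recruited" (criterion 5). Section 1 reports that "3330 patients with AD or mild cognitive impairment in 514 pedigrees were enrolled from the CFAN". In Section 6.1, "the cohort was further divided into two subgroups: autosomal dominant AD and unknown gene mutation FAD (un-FAD"). Section 3.1 places both carriers and noncarriers in the autosomal dominant (ADAD) cohort, so membership follows the family.

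The only model in Section 8 that could absorb clustering is the Bayesian linear mixed model. It is reserved for longitudinal repeated data, and no family term is named in it.

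**The concern.** Relatives share genes and environment, and the study is built on that premise: Section 4.3 requires co-segregation and Section 6.6 sets each person's visit interval from the parental or pedigree age at onset. Markers measured in several members of one pedigree are therefore likely to be positively correlated. The t-test, ANOVA, Kruskal-Wallis, chi-square and the usual correlation tests count each relative as a full independent observation.

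The direction of the error depends on the comparison:

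- **Between pedigrees** (all analysed members of a family fall in the same group, as in ADAD versus un-FAD): standard errors are too small, and false-positive differences are too frequent.
- **Correlations:** also inflated when both variables cluster within families, but less.
- **Mixed at random within pedigrees:** close to nominal.
- **Balanced within pedigrees** (for example, half of each family carriers): conservative, so power is lost.
- **Frequencies counted per pedigree**, as in Section 1: unaffected.

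The main risk is that differences between ADAD and un-FAD families are declared significant more often than the stated 5%, with confidence intervals that are too narrow.

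**Working it through.** **Inputs.**

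- Level 0.05 (Section 8). Sidedness is not stated; two-sided is assumed.
- Relatives analysed per pedigree, m: not given. Values used are 2, 4 (illustrative) and 3330/514 = 6.48 (Section 1). The last is a proxy, because it counts affected patients in an earlier report and not members with a given marker.
- ICC: not given. Values from 0.01 to 0.5 are assumed.

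**Formulas for a between-pedigree contrast, equal cluster sizes.**

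- Design effect: DE = 1 + (m − 1) × ICC
- True size = 2 × [1 − Φ(1.96/√DE)]
- Correct interval width relative to the naive one = √DE

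**Reproducing the plan's figure.** With m = 1 or ICC = 0, DE = 1 and the size is 5.0%, the stated level.

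**Example.** For m = 6.48 and ICC = 0.1, DE = 1 + 5.48 × 0.1 = 1.548 and √DE = 1.244. Then 1.96/1.244 = 1.575, and the size is 11.5%.

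**True size of the nominal 5% test:**

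| m | ICC 0.01 | 0.05 | 0.1 | 0.2 | 0.5 |
|---|---|---|---|---|---|
| 2 | 5.1% | 5.6% | 6.2% | 7.4% | 11.0% |
| 4 | 5.3% | 6.8% | 8.6% | 12.1% | 21.5% |
| 6.48 | 5.6% | 8.2% | 11.5% | 17.6% | 31.1% |

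**Interval width factor:**

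| m | ICC 0.01 | 0.05 | 0.1 | 0.2 | 0.5 |
|---|---|---|---|---|---|
| 2 | 1.00 | 1.02 | 1.05 | 1.10 | 1.22 |
| 6.48 | 1.03 | 1.13 | 1.24 | 1.45 | 1.93 |

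**Simulation with varying cluster size.** Pooled t-test, 6,000 replicates, cluster size 1 + Poisson(mean − 1), 67 versus 447 pedigrees. The split is an assumption: it treats the 13.12% missense pedigrees of Section 1 as ADAD and all others as un-FAD. Monte Carlo standard error is 0.3 to 0.6 points.

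| Mean m | ICC 0.01 | 0.05 | 0.1 | 0.2 | 0.5 |
|---|---|---|---|---|---|
| 2 | 5.4% | 5.6% | 6.7% | 7.9% | 13.8% |
| 4 | 5.4% | 7.6% | 9.7% | 13.8% | 25.5% |
| 6.48 | 5.8% | 8.3% | 12.0% | 18.3% | 33.0% |

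**Equal-size simulation checks** (67 versus 447 pedigrees). At m = 6 the t-test rejected 10.8%, 21.7% and 29.4% of the time at ICC 0.1, 0.3 and 0.5 (4,000 runs each). One 4,000-run cell, m = 2 with ICC 0.1, came out at 4.9% against 6.2% by formula; a 40,000-run repeat gave 6.1%, so the low value was chance.

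**Other tests.**

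- At m = 6 and ICC 0.3 (2,000 runs each), Kruskal-Wallis rejected 20.6% and chi-square on a dichotomised trait 16.2%.
- For Pearson correlation of two unrelated variables that both have the stated ICC, the sizes over ICC 0.01 / 0.05 / 0.1 / 0.2 / 0.5 were 4.9 / 4.5 / 5.1 / 5.4 / 9.8% at mean 2 and 5.2 / 5.0 / 5.9 / 8.1 / 22.7% at mean 6.48.
- Groups mixed at random within pedigrees stayed at 4.4% to 5.4%.
- For groups balanced within pedigrees, size = 2 × [1 − Φ(1.96/√(1 − ICC))], which gives 4.9 / 4.4 / 3.9 / 2.8 / 0.6%.

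**Does accounting for pedigree repair it?** A t-test on pedigree means, in the same kind of simulated data, rejected 4.1% to 5.2% of the time over m = 2, 3, 6 and ICC 0 to 0.5.

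**The case against.** **The contrast is inferred.** Section 8 never names ADAD versus un-FAD. The comparisons the protocol describes most directly are carrier versus noncarrier and cognitive stages within families, which are not inflated. Inclusion criterion 4, read literally, would even exclude un-FAD families. The first part stands as a limit on reach. However, Sections 3.1 and 6.1 both set up the two cohorts, and the rule for two-group comparisons covers them. For balanced carrier contrasts the same tests err the other way and lose power.

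**The size is unknown.** This stands. Lumbar puncture is optional at baseline (Section 6.5: "follow-up phone call (if participate in LP")) and, like MRI, has its own exclusions in Section 6.3, so about two relatives per pedigree is plausible for CSF or imaging. With m = 2 and ICC up to 0.1, the true size is only 6.2%, or 6.7% with varying cluster size.

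**The simulated split is imprecise.** The percentages in Section 1 do not give whole numbers of 514 pedigrees (13.12% is 67.4) but do fit 404 (53, 15 and 336). This is correct but immaterial: with 53 versus 351 pedigrees as well as 67 versus 447, the size is about 7% to 14% at mean 2 and 12% to 34% at mean 6.48 for ICC 0.1 to 0.5. The formula does not use the split.

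**This is SAP detail.** The choice among clustered methods commonly is, and a mixed model described only by its fixed effects may still contain a family term. But Section 8 does not leave the cross-sectional method open. It prescribes unadjusted tests, and a SAP that adjusted for pedigree would depart from it.

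**Conclusion.** The concern holds and should be fixed. Followed as written, Section 8 gives p-values that are too small and intervals that are too narrow for between-pedigree contrasts whenever more than one relative is analysed and the ICC is positive.

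That the plan omits clustering is certain from the text. How much it matters is a range: slight if about two relatives per family have the marker and the ICC is low, and severe if most relatives do and the ICC is high, when the true error rate can reach several times the nominal 5%. The figures rest on assumed ICCs, assumed cluster sizes and a two-sided test.

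**What to change.** Add to Section 8:

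> Cross-sectional comparisons that include more than one member of a pedigree use a linear or logistic mixed model with a pedigree random intercept, GEE with pedigree as the cluster, or pedigree-cluster-robust standard errors. Correlations that include more than one member of a pedigree take their intervals from a bootstrap that resamples whole pedigrees. The independent-sample tests are used only where one member per pedigree is analysed.

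Two details are worth settling at the same time: a clustered counterpart for the Kruskal-Wallis and Dunn branch, for which the whole-pedigree bootstrap would serve, and a small-sample correction for GEE or robust standard errors where few ADAD pedigrees have the marker.

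For each marker, report the number of members analysed per pedigree and the estimated intra-pedigree correlation.

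The cost is wording, modestly more analysis work, and wider intervals for between-pedigree contrasts. No new participant data are needed, because Section 6.5 already includes "Collecting family history and draw family tree". One point must be confirmed: the participant codes described in Section 9.2 (project, site, individual) and Appendix 1 (province, hospital, participant) contain no family code. If the analysis dataset has no pedigree identifier from elsewhere, relatives would have to be linked from the family trees across the 68 centres, and the cost would be higher.
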